8.14.2. ESRS II

The second subscale (ESRS II) is a 17-item questionnaire to evaluate parkinsonism and akathisia.

ESRS II consists of the following parts:

1. Tremor: scored on a 7-point item scale for 8 parts of the body. For each part of the body, frequency and amplitude are selected, assigning each one of the 8 items a score from 0=none to 6=severe. Therefore, the total score for tremor can ranged from 0 to 48.
2. Bradykinesia: scored on a 7-point item scale (0-6).
3. Gait and Posture: scored on a 7-point item scale (0-6).
4. Postural stability: scored on a 7-point item scale (0-6).
5. Rigidity: scored on a 7-point item scale (0-6) for 4 parts of the body. Therefore, the total score for rigidity can ranged from 0 to 24.
6. Expressive automatic movements: scored on a 7-point item scale (0-6).
7. Akathisia: scored on a 7-point item scale (0-6).

The total score of the 17 items can ranged from 0 to 102.

Total score will be the sum of the 17 items. Missing item will be replaced by the average of the remaining responses within each item.

Total score and total scores change from baseline will be summarized by time point, using descriptive statistics for continuous variables.

Data will be listed.

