### **Section 7.2 Safety Rating Scales**

In the event of an emergency situation (eg, the COVID-19 pandemic), in case a patient cannot return to the clinic for the scheduled visits (eg, due to quarantine, isolation, patient's concern, or closure of the site clinic), remote assessment of safety scales may be allowed for the following:

- via a phone call, supported by nonrecording live video for the C-SSRS (mandatory) and for the Extrapyramidal Symptom Rating Scale (ESRS), which should be completed as much as possible; some fields [ie, rigidity, stability] may be left blank as they cannot be assessed remotely; the pull test should not be done due to safety

considerations. The results of the questionnaires will be entered to the case report form (CRF) per the usual process indicating that the rating has been performed remotely.

- via iPhone or via paper back-up copy instead of iPad for Child Behavior Checklist [for ages 6-18] [CBCL] and for Epworth Sleepiness Scale [for children and adolescents] [ESS].

The results of the questionnaires will be transferred to CRF per the usual process (either from iPhone or from paper back up copy).

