6.2.2.6. Unified Huntington's Disease Rating Scale-Total Motor Score

UHDRS-TMS comprises a broad assessment of features associated with Huntington's Disease. The TMS component of UHDRS comprises 31 assessments from the 15 items of the UHDRS. The TMS is calculated as the sum of the 31 motor assessments, each of which range between 0 to 4. The minimum score is 0 (absent) and the maximum score is 124 (worst).

UHDRS-TMC is part of the UHDRS-TMS assessment and assesses the severity of chorea in the face, mouth, trunk, and the 4 extremities. The minimum score is 0 (absent), and the maximum score is 28 (marked/prolonged).

UHDRS-TMD is part of the UHDRS-TMS assessment and assesses the severity of dystonia in the trunk and the 4 extremities. The minimum score is 0 (absent), and the maximum score is 20 (marked/prolonged).

If responses of up to 25% of items are missing in UHDRS-TMS, UHDRS-TMC, or UHDRS-TMD ("scale"), the missing responses will be replaced by the average of the remaining responses within each of the scales. If 8 or more of the items are missing, the missing items will not be replaced and the scale will be set to missing.

The actual values and change from baseline for the UHDRS-TMS, TMC and TMD will be summarized.

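### The ESRS missing-item rule has no limit and no clear averaging unit, so a remote visit with rigidity and stability blank can give an undefined or wrong ESRS II total, in either direction

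*SAP*

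**What the plan says.** SAP 8.14.2 describes ESRS II as follows: "The second subscale (ESRS II) is a 17-item questionnaire to evaluate parkinsonism and akathisia", and "The total score of the 17 items can ranged from 0 to 102". Two of its parts have several items: "Tremor: scored on a 7-point item scale for 8 parts of the body" and "Rigidity: scored on a 7-point item scale (0-6) for 4 parts of the body". The other five parts, including postural stability, have one item each. For gaps, the rule is "Missing item will be replaced by the average of the remaining responses within each item". No maximum number of missing items is set. SAP 8.14.1 applies the same sentence to the 7-item ESRS I. SAP 4.3 points to Section 8 for missing-item rules, and Section 8 has no other rule for the ESRS. Totals and their changes from baseline are summarised by time point, and the data are listed.

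Protocol Appendix M (entry for Section 7.2) allows the ESRS by telephone with live video when an emergency keeps the patient from the clinic. It is to be completed as far as possible, but "some fields [ie, rigidity, stability] may be left blank as they cannot be assessed remotely", and the pull test is omitted. The CRF records that the rating was remote.

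The SAP treats its other multi-item scales in different ways. UHDRS imputation is conditional: "If responses of up to 25% of items are missing in UHDRS-TMS, UHDRS-TMC, or UHDRS-TMD", the gaps are filled from the rest of that scale (6.2.2.6). One missing ESS item invalidates the questionnaire (8.13). The CBCL Syndrome Scale has no score above 20 missing items, and no subscale score with one missing (8.12.2). MD-CRS parts I and II, however, are prorated for any missing items with no limit (6.2.2.1).

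**The concern.** Mean replacement is tolerable when a few items are missing for reasons unrelated to their values. Here the protocol identifies in advance which items may be missing, and they go missing together: the signs that cannot be rated over video. Nothing in the observed items stands in for them, and two thirds of the observed items (8 of 12) measure tremor.

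The ESRS is a listed endpoint for the primary objective. Protocol 7.1.6 names no adverse events of special interest and relies on standardised scores to monitor drug-induced parkinsonism. A change from a complete baseline to a partly imputed remote total mixes clinical change with a change in what was measured. The by-visit tables show only totals, so a reader could not tell the two apart.

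**Working it through.** **Reproducing the plan's figure.** Items: tremor 8 + bradykinesia 1 + gait and posture 1 + postural stability 1 + rigidity 4 + expressive automatic movements 1 + akathisia 1 = 17. Each scores 0 to 6, so the maximum is 17 × 6 = 102, as the SAP states.

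**What can be blank.** Rigidity 4 + postural stability 1 = 5 items. 5/17 = 29.4%, worth 5 × 6 = 30 points. The remaining 12 items have a maximum of 12 × 6 = 72.

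**Reading 1: average within each part.** Rigidity has no observed item left, and postural stability has only one item to begin with. No replacement value exists, and the SAP does not say what happens to the total.

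**Reading 2: average across the scale.** Let S be the sum of the 12 observed items and B the true sum of the 5 blank ones.

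- True total = S + B
- Imputed total = S + 5 × S/12 = 17S/12
- Error = 5S/12 − B = 5 × (mean of observed items − mean of blank items)

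The total is too low when the blank items are worse on average than the observed ones, too high in the opposite case, and right only when the means agree. Item scores below are assumed for illustration, with severity as given at the visit:

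| Profile | S | B | True | Imputed | Error |
|---|---|---|---|---|---|
| Rigidity 3 × 4, stability 3, other items sum to 6 | 6 | 15 | 21 | 8.5 | −12.5 |
| Rigidity 2 × 4 only | 0 | 8 | 8 | 0 | −8 |
| New rigidity 2 × 4 and stability 2, rest 0 | 0 | 10 | 10 | 0 | −10 |
| All items 2 | 24 | 10 | 34 | 34 | 0 |
| Tremor 2 × 8 only | 16 | 0 | 16 | 22.67 | +6.67 |
| Extremes | 0 or 72 | 30 or 0 | 30 or 72 | 0 or 102 | −30 or +30 |

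**Against the SAP's UHDRS limit.** 0.25 × 17 = 4.25, so at most 4 ESRS II items could be missing, and 5 would make the total missing. The limit alone is not enough: with stability scored and all rigidity blank, 4/17 = 23.5% passes, and rigidity would still be filled from other signs. For ESRS I, 0.25 × 7 = 1.75, so at most 1 item.

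**Which record is analysed.** Appendix M (entry for Section 3.5) requires the week 53/ET and week 54 assessments to be done in clinic after a remote visit. After a remote week 3, 7, 14, 27 or 40 visit, the return is an unscheduled visit whose assessments are agreed with the medical monitor. Protocol Table 5 makes the ESRS discretionary at unscheduled visits. SAP 4.4 selects the scheduled record when the window contains one. For weeks 3 to 40, therefore, an imputed remote total would be used even if a complete in-clinic rating followed.

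**The case against.** The case for leaving the rule alone has five parts.

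- **Frequency.** Appendix M says the fields may be blank, not that they will be. Remote visits are for emergencies, need the medical monitor's prior approval, and lapse once a site returns to normal. Sites may also hold the dose and wait for a clinic visit. A reader might infer from the 2020 to 2022 enrolment that many records are affected. The documents give no count, so that does not follow.
- **Dependence on the reading.** A numerical error arises only if averaging is across the scale. Under the by-part reading the total is undefined, not wrong.
- **Direction.** A reader might infer that the parkinsonism score falls at every remote visit and so conceals the signal. The table does not support that: the error can be zero or positive.
- **Other safeguards.** Investigators review scales for adverse events, neurological worsening is recorded as an adverse event, ESRS data are listed, and no test or decision rule uses the ESRS mean.
- **Internal practice.** MD-CRS is also prorated without a limit, so this SAP has no uniform cap that the ESRS breaks. Appendix M foresees a possible SAP amendment for COVID-19 effects.

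The first, third and fourth points stand and limit the weight of the finding. The second shows that the rule must be clarified, since neither reading gives a sound total. The MD-CRS precedent does not meet the ESRS problem, in which whole parts of the scale may be blank. A possible amendment is not a rule, and the SAP contains none for remote ESRS ratings.

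**Conclusion.** The point holds as a defect in the rule, of unknown frequency and variable direction. Following the SAP as written, a remote visit with rigidity and stability blank gives either no defined ESRS II total or one whose error is five times the gap between the observed and blank item means, at most 30 points either way. The downward case matters more for a safety scale, because emerging rigidity or instability with little else can be understated or missed in the summary.

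This rests on three assumptions: the stability field in Appendix M is the postural stability item, baseline is complete, and both fields are wholly blank. The profiles are illustrations, not estimates. The documents do not support saying that these items are blank at every remote visit or that the summary is biased in one direction. For weeks 53/ET and 54 the in-clinic repeat reduces the problem, though the documents do not say how the repeat is labelled for visit selection. ESRS I shares the unlimited wording, but Appendix M names no ESRS I field as likely to be blank.

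**What to change.** Amend SAP 8.14.1 and 8.14.2 before database lock:

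1. State the unit over which the average is taken.
2. Do not impute a part that is entirely blank (all four rigidity items, or postural stability). Set the ESRS II total to missing in that case, and also when more than 25% of its items are missing (5 or more of 17).
3. Give ESRS I the same 25% limit (no more than 1 of 7 missing).
4. For visits with rigidity and stability blank, summarise the 12-item subtotal (0 to 72) and its change from the same 12 items at baseline. Identify these visits with the remote marker already in the CRF.

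The cost is a short text change and one derived variable. Some remote totals become missing, so the number contributing at those visits falls. The subtotal keeps their information on a like-for-like basis but says nothing about rigidity or stability, and the table should state this. No new data collection is needed.

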#### **7.1.6. Protocol-Defined Adverse Events of Special Interest**

No protocol-defined adverse events of special interest for expedited reporting were identified for this study. Events of drug-induced parkinsonism, changes in behavior, and sleepiness will be monitored using standardized scores and presented as part of safety analysis (see Section 7.2).

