### 7.2.2. Extrapyramidal Symptom Rating Scale

The ESRS was designed to assess 4 types of drug-induced movement disorders: parkinsonism, akathisia, dystonia, and TD ([Chouinard and Margolese 2005](#)). In this study, parkinsonism and

akathisia will be evaluated with subscales I (subjective questionnaire) and II (evaluation for parkinsonism/akathisia). The ESRS is administered at the day 1 visit ([Table 4](#)) and administered at weeks 3, 7, 14, 27, 40, 53/ET, and 54/follow-up visits ([Table 5](#)).

Subscale I of the ESRS questionnaire rates subjective parkinsonism/akathisia at periods other than the day of examinations during the last 7 days. It is scored on a 4-point scale (0=Absent, 1=Mild, 2=Moderate, or 3=Severe). The evaluation takes into account the verbal report of the patient on the following: 1) the frequency and duration of the symptom during the day, 2) the number of days the symptom was present during the last week, and 3) the subjective evaluation of the intensity of the symptom by the patient.

Subscale II of the ESRS questionnaire for evaluation of parkinsonism and akathisia includes 17 items with scores ranging from 0 to 102 to assess the following: tremor (0 to 48), gait and posture (0 to 6), postural stability (0 to 6), rigidity (0 to 24), expressive automatic movements (0 to 6), bradykinesia (0 to 6), and akathisia (0 to 6).

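### ESRS II is summarised only as a 17-item total, so no planned ESRS summary isolates akathisia, one of the two harms the scale is used to assess

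*SAP*

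**What the plan says.** The ESRS (subscales I and II) is a safety endpoint under the primary objective (Protocol 2.1; SAP Table 1). Of the four disorders the scale was designed for, Protocol 7.2.2 keeps two, parkinsonism and akathisia: "akathisia will be evaluated with subscales I (subjective questionnaire) and II (evaluation for parkinsonism/akathisia". SAP 8.14.2 agrees: "The second subscale (ESRS II) is a 17-item questionnaire to evaluate parkinsonism and akathisia".

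SAP 8.14.2 lists seven parts with their score ranges, sums all 17 items, and plans this summary: "Total score and total scores change from baseline will be summarized by time point, using descriptive statistics for continuous variables". The data are also to be listed. SAP 8.14.1 handles ESRS I in the same way, with a 7-item total that by its own description spans parkinsonism, akathisia, dystonia and dyskinesia. Neither the SAP nor Protocol 9.6 plans a part score, category count or shift table for any component of the ESRS.

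**The concern.** A scale used to assess two harms should yield a readable result for each. The planned total does not do so for akathisia, which is one item among 17. Nor is the total a clean parkinsonism score, because akathisia is included in it.

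The risk is one of interpretation. A flat or slightly falling ESRS II total may be taken to mean that no extrapyramidal problem emerged, although it says very little about akathisia specifically. The other subscale does not fill the gap, because it is pooled as well.

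**Working it through.** **Inputs** (SAP 8.14.2; Protocol 7.2.2 gives the same part ranges). Every item is scored 0 to 6, higher being worse.
- Tremor, 8 items: "Therefore, the total score for tremor can ranged from 0 to 48"
- Rigidity, 4 items: "Therefore, the total score for rigidity can ranged from 0 to 24"
- Bradykinesia, gait and posture, postural stability, expressive automatic movements and akathisia: 1 item each, 0 to 6
- Total: "The total score of the 17 items can ranged from 0 to 102"
- Planned enrolment: about 45 (SAP 2.5)

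**Reproducing the plan's figure.** Items: 8 + 1 + 1 + 1 + 4 + 1 + 1 = 17. Maximum: 17 × 6 = 102, which agrees with the SAP.

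**Share of the maximum.**
- Tremor: 48/102 = 47.1%
- Rigidity: 24/102 = 23.5%
- Akathisia: 6/102 = 5.9%

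**After separation.** Akathisia is 1 item, 0 to 6. The remaining items are 17 − 1 = 16, with range 0 to 16 × 6 = 96. Check: 96 + 6 = 102.

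**Dilution (assumed rises, other items unchanged).** If m of 45 patients each rise by s points on akathisia, the mean total rises by m × s / 45.

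| Patients rising (m) | Points (s) | Rise in mean total | Rise as % of 102 |
|---|---|---|---|
| 1 | 2 | 0.04 | 0.04% |
| 5 | 4 | 0.44 | 0.44% |
| 9 | 6 | 1.20 | 1.18% |

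**Offset.** In the middle row, the rise disappears from the mean if the other 16 items fall by 0.44 points in total, or 0.44/16 = 0.028 points per item on average.

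**Other planned outputs.** SAP 4.1 defines the continuous summary as n, mean, SD, SE, median, minimum and maximum. In the middle row the maximum change in the total would be at least 4, unless those same patients improved on other items. It would show that someone's total rose, but not which item caused the rise.

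**The case against.** The case for leaving the plan alone has real content.

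- **Akathisia can surface elsewhere.** Protocol 7.2 has investigators review every scale for reportable adverse events and compare scores with baseline. SAP 8.3 counts patients by preferred term. SAP 8.14.2 lists the data, and an IDMC reviews accumulating safety data. This stands, and a reader who inferred that the plan cannot report emergent akathisia would be going too far. But these routes depend on site recording or on reading listings, and none gives a by-visit or change-from-baseline summary from the scale.
- **The analysis text names only parkinsonism.** Protocol 7.1.6 says: "Events of drug-induced parkinsonism, changes in behavior, and sleepiness will be monitored using standardized scores and presented as part of safety analysis". Protocol 9.6 likewise ties the ESRS to drug-induced parkinsonism. This also stands: the commitment to akathisia is in the assessment sections (Protocol 7.2.2, SAP 8.14.2), not in those two. Even so, the 17-item total is not a parkinsonism score, so separating the items serves both wordings.
- **Shares of a theoretical range are not shares of observed score or variance.** Correct. The documents give no baseline tremor values and no reason to expect tremor to fall, so masking is a possibility and not a prediction.

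Two further inferences are not supported. The first is that akathisia and bradykinesia, being opposite kinds of movement, cancel in the total. All items score upward with severity, so a patient who develops both gains on both; an offset needs some other item to improve. The second is that only a mean is reported. SAP 4.1 also gives the spread, median and extremes, though only for the total.

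**Conclusion.** The point holds as a gap in planned reporting. No summary planned from either ESRS subscale isolates akathisia, although both documents say the scale evaluates it. The item carries 5.9% of the ESRS II range. Under the assumed rises, between 1 patient gaining 2 points and 9 patients gaining 6, the mean total moves by 0.04 to 1.20 points out of 102.

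The range shares are exact. The illustration rests on 45 patients, on assumed rises, and on no change in the other items. The study is descriptive, so no sample size, error rate or power is affected. The change is worth making because the ESRS serves the primary objective, the item scores are already collected, and the SAP already reports another multi-part safety scale by subscale (CBCL, SAP 8.12.2).

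**What to change.** In SAP 8.14.2, summarise the following by visit, with change from baseline:
1. the akathisia item (0-6);
2. the parkinsonism score, the sum of the other 16 items (0-96);
3. the part scores the section already lists;
4. the 17-item total (0-102), kept as an additional row.

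Optionally, add a shift table from baseline to the worst on-treatment value for akathisia, bradykinesia and rigidity. Three safeguards are needed:
- Use observed values only. Protocol Appendix M lets rigidity and stability be left blank at remote visits, and SAP 8.14.2 replaces missing items with an average.
- Show week 54 separately, because the drug has been stopped by then.
- State that worst-value counts without a control arm include ordinary rating fluctuation. For the same reason, a bare count of patients with any increase would be a poor substitute, since a single 1-point rise at one visit would qualify.

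The cost is a few more table rows. No data collection, visit or clinical procedure changes.

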9. TOLERABILITY VARIABLES AND ANALYSIS

If more than 15% of the patients withdraw from the study before the end of the treatment period, the number of days until study discontinuation will be analyzed using Kaplan-Meier methodology with the ITT analysis set.

10. STATISTICAL SOFTWARE

All data listings, summaries, and statistical analyses will be generated using SAS® version 9.4 or later.

**11. CHANGES TO ANALYSES SPECIFIED IN THE STUDY
PROTOCOL**

Not applicable.

